## INNOVATION

Our approach represents a major leap forward in the inexpensive and noninvasive screening of OPD, through use of novel theoretical concepts and technologies and objective decision-making methods that will mitigate dysphagia-related adverse events in ordinary clinical scenarios, while at the same time directing resources to gold standard diagnostic testing only for those patients who need it [37]. Our goal is to develop a novel screening paradigm using the Aspirometer, as a universal OPD screening tool that can be deployed in ordinary and often chaotic clinical settings like hospital emergency rooms, nursing homes, and home care

**Figure 3 – SIS pathways with and without HRCA.**

	OPD screening protocols	VF	Cervical auscultation	HRCA (proposed approach)
Excellent accuracy		✓		✓
Affordable	✓		✓	✓
Easily administered	✓		✓	✓
Silent aspiration		✓		✓

**Figure 4 – The significance of the proposed work.**

situations [38, 39], where OPD is prevalent and imaging studies are unavailable or unacceptable to the patient. But that leap requires our further engineering and clinical developments to enable an HRCA system to predict which patients need protective interventions to mitigate their pneumonia risk.

In our currently R01 funded research, we have established moderate but significant relationships between swallow kinematic events observed via VF and the HRCA signals they generated (see section A2.c) as well as correlations between HRCA signals and airway protection, a key predictor of aspiration pneumonia. Our findings have advanced the science of OPD early detection beyond that of previous studies that have not culminated into integration of these findings to characterize actual risk of OPD-related adverse events like AP [40-58]. These earlier studies attempted to match VF images to CA signals to associate swallow events to sounds [59, 60], or infer the relation between kinematic events and key features of the swallowing signal [27, 61-64]. But unlike our research, none of these studies has directly linked distinct waveform features to underlying swallow physiology or silent aspiration, and they have established only the presence of weak correlations between swallow events and signals [60, 64] (Figure 5).

Our approach breaks new ground by equating swallow physiologic data collected in ordinary settings to accepted metrics of swallow impairment, and defining HRCA outputs that can identify patients in need of intervention without the use of VF imaging.

**Table 1** – The innovation of the proposed project. SIS denotes standardized institutional screening.

[figure not shown]
Open questions	Current state-of-the-art	Proposed research
Define the HRCA range of “normal swallowing signals” from healthy people	Our large data set from 4000 swallows of people referred for dysphagia testing has been analyzed; no “healthy data”; prior studies of “normal” used different signal processing and data collection methods	Collect and analyze swallows from healthy persons; repeat analyses performed on 4000 swallow data set from patients; completes the range of data collected from healthy → severely dysphagic
Equate the HRCA signal results to accepted standard of swallow impairment	Not understood; prior research has equated signals and signal features to specific events and not to accepted, clinically utilized and validated measures of swallow impairment	Rate all swallows in both data sets (4000 swallows from patients + swallows from healthy people) with the “Modified Barium Swallow Impairment Profile”
Can HRCA identify dysphagia more accurately than SIS?	Can differentiate grossly abnormal from normal. Demonstrated only for small sample sizes. Not clinically validated.	Deploy a HRCA system; blinded, randomized controlled trial comparing SIS to SIS + HRCA, using videofluoroscopy as the gold standard

OPD impairment using robust big-data analysis approaches, not previously used in this line of research. Third, we will test our HRCA-based Aspirometer system in a blinded, randomized controlled trial comparing the outcomes of SIS with and without our HRCA-based tool.

## APPROACH

**PROGRESS REPORT FOR RENEWAL:** The project (July 2013-June 2018) revolved around the following aims:

- 1) **In order to accumulate an adequately-powered reference data set for training signal processing classifiers, we will collect swallowing accelerometry signals from a larger sample of individuals undergoing concurrent videofluoroscopy.**
- 2) **In order to enhance the accuracy of signal processing classification algorithms to detect problems in swallowing safety and efficiency, we will add an additional physiological signal to the Aspirometer design (acoustic information, collected concurrently with a co-located microphone). We will explore the value of any non-overlapping information in this additional signal for improving the accuracy of the classifier.**

**Figure 5** – Some established relationships between HRCA and swallowing kinematic events found in the literature [24].

weak correlations between swallow events and signals [60, 64] (Figure 5).

Our approach breaks new ground by equating swallow physiologic data collected in ordinary settings to accepted metrics of swallow impairment, and defining HRCA outputs that can identify patients in need of intervention without the use of VF imaging.

**Table 1** – The innovation of the proposed project. SIS denotes standardized institutional screening.

Open questions	Current state-of-the-art	Proposed research
Define the HRCA range of “normal swallowing signals” from healthy people	Our large data set from 4000 swallows of people referred for dysphagia testing has been analyzed; no “healthy data”; prior studies of “normal” used different signal processing and data collection methods	Collect and analyze swallows from healthy persons; repeat analyses performed on 4000 swallow data set from patients; completes the range of data collected from healthy → severely dysphagic
Equate the HRCA signal results to accepted standard of swallow impairment	Not understood; prior research has equated signals and signal features to specific events and not to accepted, clinically utilized and validated measures of swallow impairment	Rate all swallows in both data sets (4000 swallows from patients + swallows from healthy people) with the “Modified Barium Swallow Impairment Profile”
Can HRCA identify dysphagia more accurately than SIS?	Can differentiate grossly abnormal from normal. Demonstrated only for small sample sizes. Not clinically validated.	Deploy a HRCA system; blinded, randomized controlled trial comparing SIS to SIS + HRCA, using videofluoroscopy as the gold standard

OPD impairment using robust big-data analysis approaches, not previously used in this line of research. Third, we will test our HRCA-based Aspirometer system in a blinded, randomized controlled trial comparing the outcomes of SIS with and without our HRCA-based tool.

## APPROACH

**PROGRESS REPORT FOR RENEWAL:** The project (July 2013-June 2018) revolved around the following aims:

[figure not shown]
- 1) **In order to accumulate an adequately-powered reference data set for training signal processing classifiers, we will collect swallowing accelerometry signals from a larger sample of individuals undergoing concurrent videofluoroscopy.**
- 2) **In order to enhance the accuracy of signal processing classification algorithms to detect problems in swallowing safety and efficiency, we will add an additional physiological signal to the Aspirometer design (acoustic information, collected concurrently with a co-located microphone). We will explore the value of any non-overlapping information in this additional signal for improving the accuracy of the classifier.**

3) In order to explore the potential of non-invasive swallowing signal processing classifiers to detect swallowing problems *beyond the context of thin liquid swallows*, we will expand our data collection protocol to include swallows of nectar-thick and honey-thick liquids.

Aim 1 was successfully completed, as we collected HRCA data from 274 patients (24 more patients than initially proposed) undergoing a concurrent VF exam. As a result, we have a unique, large database of simultaneously acquired HRCA signals and VF images that is unparalleled in OPD research.

Per Aim 2, we clearly demonstrated that multiple sound and vibrations signal features acquired simultaneously during VF exams contain complimentary information, and they should not be substituted for each other. Figure 6(A) summarizes our main results from [67]. The shaded columns and rows indicate microphone and accelerometer axis combinations with the greatest number of dissimilarities indicating the complementary nature of acoustic and vibratory signal features, while the red dots indicate signal features in which the vibratory signal features had significantly higher values than the acoustic signals. Figure 6(B) summarizes our main results of [68]. Specifically, although the swallowing sounds and swallowing vibrations might have the same kinematic sources, swallowing signals recorded by the microphone (sounds) and the accelerometer (vibrations) differed from each other in the time and frequency domains. These findings shift the existing paradigm that

swallowing sounds and vibration information are equivalent [78, 79], and support our two-sensor method as superior to a single acoustic detector [79, 80]. In fact, our findings confirm that swallowing signals from both sensors provide useful information about swallowing function. Hence, our subsequent research of swallowing physiology with these sensors using concurrent VF images advanced our understanding of the sources of swallowing-related vibrations and sounds.

**Figure 6 –** Our results for Aim 2: (A) A summary of differences between swallowing sounds and vibrations among groups of study. Red/black circles indicate that the axis/mic in “Comparison couple” column has the higher value in a specific feature mentioned in “Features” column than the mic/axis. The column highlighted in light green and five rows highlighted in light orange indicate group/features with the largest number of dissimilarities. (B) A summary of directional differences. All dots (red and black) indicated the existence of directional dissimilarities. Axes column demonstrates which two axes are compared to each other. Red dots indicate that the first axis in the axes column has a higher value of the computed feature in features column than the second axis, while black dots indicate the second axis has a higher value than the first axis.

As per Aim 3, we clearly demonstrated that swallowed fluid viscosity strongly influences the swallowing assessment (Figure 7 summarizes the main results of [70]). We found that HRCA can detect several statistical differences between unsafe swallows of viscous fluid, in which clinically significant aspiration and laryngeal penetration occurred, and safe swallows that exhibited airway protection scores that fall within the normal range for healthy people [81]. This is of interest because aspiration of thicker liquids has been shown to produce higher rates of pneumonia and longer hospitalization durations than aspiration of thin liquids [82]. Past research has suggested that thickening agents used during videofluoroscopy exams exhibit non-Newtonian fluid properties, which lead to the reduced aspiration rate in dysphagic patients [83, 84].

Based on this research by our team, [name] received the **Presidential Early Career Award for Scientists and Engineers** in 2016. Overall, the project was very successful as all three aims were successfully

completed and over 10 publications have been disseminated in major research journals [65-77], in addition to numerous presentations by [name] and [name] at domestic and international institutions/conferences. Our line of research has also begun investigating theoretical frameworks linking swallowing signals to other central and peripheral mechanisms of recent interest to researchers by investigating brain networks on a swallow-by-swallow basis using electrophysiologic monitoring [73-77]. One of our future mechanistic goals is to relate central neurological changes in disease states to features extractable from HRCA recordings to portray a complete picture of swallowing, from central neurological changes in the brain to peripheral kinematic events observed aerodigestive tract.

(A)	Thin		Viscous	
	Safe	Unsafe	Safe	Unsafe
Skewness	0.867, 1.470	0.642, 1.963	0.491, 1.455	0.759, 1.621
Kurtosis	87.04, 25.48	27.56, 29.84	96.20, 30.07	39.69, 15.85
Entropy Rate	0.987, 0.007	0.987, 0.007	0.989, 0.006	0.986, 0.004
L-Z Complexity	0.059, 0.031	0.065, 0.030	0.056, 0.039	0.064, 0.029
Peak Freq (Hz)	16.56, 4.732	7.162, 5.161	56.29, 4.414	15.22, 5.613
Center Freq (Hz)	189.7, 138.3	109.2, 115.4	204.7, 113.4	141.0, 78.93
Bandwidth (Hz)	221.1, 222.6	198.1, 158.2	273.7, 174.7	264.2, 86.94
Wavelet Entropy	1.034, 1.348	1.003, 0.976	0.928, 1.139	1.066, 1.120

(B)	Thin		Viscous	
	Safe	Unsafe	Safe	Unsafe
Skewness	-0.557, 1.082	-0.435, 2.305	-0.129, 1.207	-0.441, 0.754
Kurtosis	28.91, 14.79	101.6, 31.11	66.26, 11.13	22.68, 8.000
Entropy Rate	0.988, 0.005	0.989, 0.003	0.989, 0.006	0.988, 0.004
L-Z Complexity	0.068, 0.033	0.067, 0.032	0.062, 0.038	0.069, 0.032
Peak Freq (Hz)	11.33, 3.660	19.52, 7.336	10.79, 3.627	30.60, 3.812
Center Freq (Hz)	67.53, 47.45	143.4, 56.31	105.7, 44.94	85.52, 20.85
Bandwidth (Hz)	114.7, 99.64	238.4, 62.16	145.3, 107.5	180.4, 35.51
Wavelet Entropy	1.160, 1.178	0.978, 0.996	1.138, 1.001	1.004, 1.408

(C)	Thin		Viscous	
	Safe	Unsafe	Safe	Unsafe
Skewness	-0.317, 3.334	-1.564, 3.531	-0.525, 3.894	-0.125, 3.873
Kurtosis	149.2, 117.0	187.2, 101.0	191.8, 132.4	157.3, 88.60
Entropy Rate	0.985, 0.009	0.986, 0.009	0.987, 0.007	0.987, 0.007
L-Z Complexity	0.055, 0.031	0.055, 0.048	0.050, 0.026	0.052, 0.038
Peak Freq (Hz)	94.10, 122.3	99.52, 77.71	99.46, 130.4	92.88, 100.2
Center Freq (Hz)	312.5, 315.9	348.5, 245.7	340.3, 305.1	382.2, 294.2
Bandwidth (Hz)	348.2, 281.8	393.6, 170.0	402.7, 284.0	399.0, 230.7
Wavelet Entropy	1.723, 1.151	1.641, 1.119	1.596, 0.946	1.697, 1.615

[figure not shown]
**Figure 7 – Our results for Aim 3:** (A) Feature values corresponding to anterior-posterior swallowing vibrations. (B) Feature values corresponding to swallowing sounds. (C) Feature values corresponding to swallowing sounds. These values represent the mean and interquartile range of each feature of our data set separated by bolus viscosity and whether it was a safe or unsafe swallow. intervention or VF studies. This will help to allocate VF and intervention resources to those who currently fail dysphagia screens but are not at risk (false positives).

#### AIM 1: Complete the entire continuum of HRCA swallowing signals from normal to severely impaired, by collecting HRCA swallow data from healthy people.

**A1.a. Introduction:** The goal of a useful HRCA swallowing screening tool is to accurately distinguish healthy/normal swallowing from OPD that can pose health threats to the patient. We have a large database of 4000 swallows from patients referred for VF evaluation of dysphagia and have equated their VF-identified OPD characteristics with HRCA signal features, but we do not have data to complete the “normal” end of the impairment severity continuum from healthy people. The objective of this aim is to collect and analyze swallow VF data from healthy persons without dysphagia, extending our previous R01 project. This will complete a large, master set of swallows of all impairment severity levels, and our analysis will determine define the cutoff for “normal” (or “healthy/nonpathological”) swallows from HRCA signals. The working hypotheses for this aim is that pharyngeal swallowing events in HRCA signals from healthy people exhibit significantly different HRCA signal signature features than those from patients with dysphagia and that there is sufficient separation to allow discrimination (see A1.c.). We will use an approach that relies on modern machine learning methods [85]. We will collect a set of unimpaired swallows from healthy age-matched adults to represent the “normal” end of the OPD impairment continuum. This aim’s rationale is that our current data set’s least severely impaired swallows were obtained from patients with suspected dysphagia due to disease, and therefore are not valid representations of normal swallows from healthy people. We expect that completion of the entire continuum of impairment severity with HRCA will enable us to preemptively differentiate patients requiring more aggressive or immediate diagnostic intervention than is currently possible with SIS while more accurately identifying patients who do not require intervention. By achieving this aim we will accomplish an essential goal in healthcare associated pneumonia prevention: accurate and early detection of clinically significant OPD impairment from HRCA signals and expedited patient management in clinical and other naturalistic settings.

**A1.b. Justification and feasibility – Review of relevant literature:** Following development of the penetration-aspiration scale (PAS), it was determined that PAS scores differentiated healthy swallows from those obtained

from people with two conditions that cause OPD: stroke and treatment for head and neck cancer [81]. 71 of 95 normal participants produced PAS scores of "1" (no airway penetration) on the first and second swallows, with 19 producing a score of "2" and a single participant producing a "3" with no scores observed above "3". Meanwhile patients in both patient groups scored significantly "higher" (more severe) on the PAS than did the

**Figure 8 – PAS scores for healthy controls, stroke and cancer patients.**

normals during both first and second swallows (Figure 8). Likewise, significant kinematic differences between healthy and disordered swallows have been the benchmark for defining OPD for more than 3 decades [32, 86-89]. Studies have shown significant differences between healthy swallows and those observed in patients with OPD swallows, in the swallow kinematic events that we are measuring in this project (e.g., the duration of stage transition, oral and pharyngeal transit durations, and duration of laryngeal closure among many others) [90-92]. Because of the disparity in PAS and other measures of swallow function between controls and people with suspected OPD whose swallowing is not clinically unsafe, completion of the HRCA continuum to include normal swallows is necessary to advance our innovative approach to noninvasive OPD classification.

Past studies attempting to classify CA signals have had various limitations. First, many studies utilized less than optimal sample sizes and did not clearly differentiate independent judge training and testing groups, which limits the generalizability of the results [37, 58, 93-104]. Second, linear classifiers have possibly reduced the maximum potential accuracy of the classification method [37, 95, 96, 100-102, 105]. Finally, a number of studies incorporated measurements other than cervical auscultation (e.g., nasal airflow) [58, 93, 94, 100, 103], which introduced additional confounding variables. Our literature search found that techniques that utilize neural network-based classifiers have some of the highest reported accuracies for a given task [93, 94, 97-100, 105], but there are open problems still unresolved. These studies acknowledge that they are investigating a limited selection of mathematical signal features and that alternate choices may offer benefits to classification. From these previous attempts, the field would benefit from a technique that was both able to analyze higher-order signal features and could self-select features to analyze through use of unsupervised learning methods. One relatively new classification technique, deep learning, possess these desirable traits, thereby combining much of the past research on the topic into a single method.

**A1.c. Justification and feasibility – Preliminary studies:** In our preliminary research using an artificial intelligence method was used to differentiate swallows made by healthy subjects and the least impaired swallows produced by patients with OPD [70]. A total of 55 healthy participants (28 men, 27 women, mean age 39) with no history of swallowing disorders, head or neck trauma or major surgery, chronic smoking, or other conditions which impair swallowing performance, completed a total of 30 independent swallows of several liquid viscosities while their head was in a neutral position. The non-healthy participants consisted of a total of 53 patients (34 men, 19 women, mean age 63) with suspected dysphagia who were undergoing a VF evaluation at the discretion of the examining clinicians and based on patient needs, rather than an artificially controlled, standardized data collection procedure. Presentation order, head position, and other environmental factors were unique for each patient. The materials swallowed during the examination were of comparable consistencies (thin (<5 cps), 'nectar' (300 cps), 'honey' (2000 cps) consistency liquids) to those provided to healthy subjects based on available product information and qualitative guidelines. Using all of these swallows from both groups, we built an artificial intelligence method [70] based on deep belief networks [107], one of the newest forms of artificial neural networks [108], which combines multiple neural networks in different layers into a single decision process. Figure 9 summarizes our results. Our combined deep belief network configuration also demonstrated generally

Combination Network	Input Network	Structure			Statistical Metrics		
		Specificity	Sensitivity	Accuracy			
1-Layer	Small 1-Layer	90.7	83.7	87.2			
	Small 2-Layer	93.3	81.6	87.5			
	Small 3-Layer	90.9	82.2	86.5			
	Large 1-Layer	93.0	81.7	87.4			
	Large 2-Layer	96.9	85.7	91.3			
	Large 3-Layer	98.5	75.3	86.9			
2-Layer	Small 1-Layer	94.3	80.7	87.5			
	Small 2-Layer	92.0	83.3	87.6			
	Small 3-Layer	87.5	84.2	85.9			
	Large 1-Layer	97.5	79.7	88.6			
	Large 2-Layer	96.2	81.1	88.7			
	Large 3-Layer	97.8	77.6	87.7			
3-Layer	Small 1-Layer	91.1	83.7	87.4			
	Small 2-Layer	92.0	82.9	87.5			
	Small 3-Layer	83.3	77.4	80.3			
	Large 1-Layer	97.5	78.3	87.9			
	Large 2-Layer	95.4	78.0	86.7			
	Large 3-Layer	98.5	75.9	87.2			

**Figure 9 – Preliminary results for Aim 1.** Using different configurations of artificial neural networks, we can achieve very high accuracies. In this case, a 1-layer combination of two large 2-layer networks for each axis provided the best results (bolded above).

greater sensitivity than our single-axis networks. But we do not have concurrent VF validation of the data obtained from the healthy people. Collection and analysis of these data will complete the range of swallow function and enable completion of our 2nd and 3rd aims, which seek to develop an HRCA impairment severity continuum.

**A1.d. Experimental approach:** STEP 1: We will collect concurrent VF and HRCA recordings from 70 healthy subjects (35 females and 35 males) with no previous history of swallowing difficulties who are age matched to our database of swallows from patients with OPD. Each subject will complete five swallows of 3mL thin liquid and five swallows of self-selected, comfortable volume of thin liquid from a cup, in a head-neutral position. STEP 2: We will first measure nine kinematic measures with VF (onset, offset, and time to peak hyolaryngeal excursion; laryngeal closure and reopening; UES closure and reopening; onset and offset of tongue base to posterior wall contact), penetration-aspiration scale scores [109], and pharyngeal retention/residue scores [89, 110, 111, 112].

STEP 3: Pre-process all HRCA recordings per steps taken in previous publications [29, 30, 71], to remove any disturbances and diminish noise in these recordings. STEP 4: VF results (STEP 2) will be equated with HRCA signal features and categorized by bolus volume of the swallowed material, these data will be combined with the data from over 4000 patient swallows from our previous R01 grant.

[figure not shown]

Figure 10 – Our proposed experimental and data analysis approach for Aim 1.

STEP 5: We will develop an algorithm based on the state-of-the-art machine learning concepts that will differentiate between healthy controls and people with suspected OPD whose swallows did not exhibit OPD (see Figure 10). Specifically, we will analyze a random 70% training subsample and use the deep belief machine learning approach as in our preliminary work [70]. Once modeling is complete, the remaining 30% validation subsample will be used to obtain accuracy estimates devoid of model overfitting.

**A1.e. Data interpretation:** In STEP 2, [name] will train doctoral students to evaluate all VF dependent variables and establish their inter- and intra-rater reliability (intraclass correlation coefficient above 0.9 for continuous variables and kappa above 0.75 or percent exact agreement above 80% for categorical variables), in the measurement of kinematic event timing, and assignment of P-A and pharyngeal retention/residue scores. They will use ImageJ image processing software, to measure penetration-aspiration scores, and kinematic and pharyngeal retention/residue measures from all swallow recordings in this new set of healthy swallows, and complete the same measurements from the remaining 3900 swallows in our database that did not undergo the complete kinematic analysis that we performed to produce the preliminary data presented in section A2.c. To ensure their judgments do not drift over time, we will perform ongoing reliability measures using the same criteria, through a rolling re-analysis of a randomly selected 10% of analyzed swallow recordings. Then, to understand the accuracy of the developed HRCA analysis algorithm using only the training subsample in STEP 5, we will begin by calculating a confusion matrix [85]. The confusion matrix will be calculated by comparing the algorithm's output with scores from STEP 2. The confusion matrix will be then used to calculate false positives, false negatives, true positives and true negatives, and lastly sensitivity, specificity, predictive values and likelihood ratios for the algorithm. These values will be initially calculated using the leave-one-out approach, but we will then repeat the analysis with 10-fold cross-validation. Then in STEP 5, we will use the number of correctly and incorrectly HRCA-detected swallows to calculate the sensitivity and specificity values, again using the leave-one-out approach (the most exhaustive and computationally expensive cross-validation approach) and 10-fold cross-validation. We have proposed state-of-the-art machine learning methods based on deep learning as our primary analysis, but we will also consider other techniques such as classification tree methods [113], and generalized linear models due to their ability to produce simpler prediction rules for ease of use, cognizant of the potential loss of some accuracy compared to deep learning. Finally, we will use the validation subsample to obtain authoritative measures of accuracy devoid of risks of model overfitting.

**A1.f. Expected outcomes:** The benchmark for success of Aim 1 will be creation of a machine learning algorithm that completes the continuum of of HRCA signal characteristics from normal to the most severely impaired swallowing function that will then be available for future research. Specifically, we anticipate these algorithms

will correctly identify normal airway protection (PAS scores of 1-2) in healthy controls and patients with dysphagia with over 90% accuracy compared to the gold standard VF ratings for each swallow [70]. These outcomes will establish the evidence that the HRCA signals and advanced analytics form a robust and reliable swallowing screening system with comparable accuracy to VF, while also demonstrating the system's ability to identify additional swallowing diagnostic features that are currently only possible with VF, potentially advancing HRCA as not a screening tool with diagnostic capabilities far beyond SIS.

**A1.g. Challenges and contingency plans:** The preliminary results (see A1.c.) strongly support our hypothesis (see A1.a.). In the highly unlikely event that our VF judges' ratings drift unacceptably, we will increase surveillance on inter- and intra-rater reliability and pull judges from analysis and retrain them to criterion, retest their reliability before placing them back online.

**A1.h. Sample size justification:** We currently have data on 4000 swallows from 274 dysphagic persons. We plan to add 700 swallows from 70 healthy persons to this data set. Allowing for some refusals, we anticipate obtaining 650 swallows from 65 healthy persons. Assuming the sensitivity and specificity will be approximately 90%, intra-class correlation of 0.7 from our prior data and a resulting design effect of 3.8 [114], and using published methods [115, 116] implemented in commercially available software (PASS 2012, Number Cruncher Statistical Systems, Kaysville, UT), conservatively we will be able to estimate sensitivity with a margin of error as small as  $\pm 2\%$  and specificity with  $\pm 8\%$  in the training sample, and  $\pm 3\%$  and  $\pm 13\%$  in the validation samples, at the 95% confidence level.

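### In Aim 1, healthy versus patient status is completely aliased with recording campaign, and none of the planned validation steps can tell swallowing from recording conditions

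*Combined protocol and SAP*

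**What the plan says.** **Healthy side.** A1.d STEP 1: "We will collect concurrent VF and HRCA recordings from 70 healthy subjects (35 females and 35 males"), each giving ten thin-liquid swallows in a head-neutral position. A1.h: "We plan to add 700 swallows from 70 healthy persons to this data set", with 650 swallows from 65 people expected after refusals.

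**Patient side.** A1.d STEP 4, on the new healthy recordings: "these data will be combined with the data from over 4000 patient swallows from our previous R01 grant". A1.h: "We currently have data on 4000 swallows from 274 dysphagic persons". The progress report dates that grant: "The project (July 2013-June 2018) revolved around the following aims". A1.d describes no new patient recordings for Aim 1, and Table 1 says that the existing data set holds no healthy data.

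**What is classified.** STEP 5 separates healthy controls from people with suspected OPD whose swallows did not show OPD. A1.e compares the algorithm's output with the STEP 2 VF scores. A1.f sets a benchmark of over 90% accuracy for PAS 1-2 in both groups.

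**Validation and controls.** There is a random 70/30 split, leave-one-out and 10-fold cross-validation. A1.e treats the 30% subsample as the decisive accuracy measure. The stated controls are age matching, common pre-processing (STEP 3), categorisation by bolus volume (STEP 4) and checks on VF rater reliability. The only challenge named in A1.g is rater drift.

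**Later use.** A3.d STEP 3 applies the findings of Aims 1 and 2 to 50 new patients, recorded while they swallow water during the SIS, with VF done separately within 24 hours. A3.e compares c-statistics by DeLong's method.

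**The concern.** A flexible classifier uses whatever separates its two classes. Here one class was recorded under one grant and the other will be recorded under its renewal. Any systematic difference in equipment, room, background noise or task conduct is therefore available as a group cue, in addition to any swallow difference. STEP 5 also contrasts healthy people with patients whose swallows looked unimpaired, where the true swallow signal is likely to be small and a nuisance cue would count for most.

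The documents treat acquisition differences as important. Table 1 sets aside earlier studies of normal swallowing because they "used different signal processing and data collection methods". In the A1.c pilot the patients were examined under clinical conditions: "Presentation order, head position, and other environmental factors were unique for each patient". Of the pilot's healthy group A1.c says: "But we do not have concurrent VF validation of the data obtained from the healthy people". The pilot's 91.3% accuracy therefore also compares two recording settings, and it cannot rule out a contribution from the setting.

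Two things are at stake. The Aim 1 accuracy could be reported as swallow discrimination when part of it is not. The algorithm carried into Aim 3 could also give weight to a cue that tells nothing about OPD among patients recorded under one set of conditions.

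**Working it through.** **1. Class by campaign (A1.d, A1.h, Table 1).** The plan's counts reproduce: 70 × (5 + 5) = 700 healthy swallows planned, and 65 × 10 = 650 expected.

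| | Earlier grant | New recordings |
|---|---|---|
| Patient swallows | 4000 | 0 |
| Healthy swallows | 0 | 650 (700 planned) |

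Both off-diagonal cells are empty. For the STEP 5 label, class and campaign are the same variable.

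**2. Other targets.** For PAS 1-2 versus 3-8 (A1.e, A1.f) the label varies among patients, so the alias is incomplete. It is still present: A1.b cites a healthy sample with no PAS score above 3, so new-campaign swallows would fall almost entirely in the normal class.

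**3. Validation.** A random 30% of the pooled data has the same two empty cells, and so does every leave-one-out or 10-fold partition. Splitting by person does not change this.

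**4. Possible size.** The campaign shift is not in the documents; the values below are assumptions. Take two independent unit-variance cues: a swallow cue with shift d0 and a campaign cue with shift d.

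- True c = 0.70 gives d0 = √2 × Φ⁻¹(0.70) = 0.742, so d0² = 0.550.
- The optimal linear score separates the Aim 1 classes by D = √(d0² + d²), so apparent c = Φ(D/√2).
- Within a single campaign only the swallow cue separates people. If OPD and non-OPD patients differ by the same d0, c = Φ(d0²/(D√2)).
- With no swallow signal at all, apparent c = Φ(d/√2).

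| d (SD) | D | Apparent Aim 1 c | c within one campaign | Apparent c, no swallow signal |
|---|---|---|---|---|
| 0 | 0.742 | 0.70 | 0.70 | 0.50 |
| 0.5 | 0.894 | Φ(0.632) = 0.74 | Φ(0.435) = 0.67 | Φ(0.354) = 0.64 |
| 1 | 1.245 | Φ(0.880) = 0.81 | Φ(0.312) = 0.62 | Φ(0.707) = 0.76 |
| 2 | 2.133 | Φ(1.508) = 0.93 | Φ(0.182) = 0.57 | Φ(1.414) = 0.92 |

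**5. Does a hold-out reveal it?** A simulation used 274 patients × 15 swallows, 65 healthy people × 10 swallows, ICC 0.7, a random 70/30 split by person and a logistic classifier. With no true signal, the hold-out c was 0.50, 0.65, 0.76 and 0.92 for shifts of 0, 0.5, 1 and 2 SD. The hold-out confirms the spurious result.

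**6. Fixed cutoff in Aim 3.** The same simulation, with a true swallow shift of 1 SD and a predicted-probability cutoff of 0.5, gave:

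| Campaign shift (SD) | Aim 3 resembles healthy campaign: sens / spec | Aim 3 resembles earlier grant: sens / spec |
|---|---|---|
| 0 | 0.72 / 0.71 | 0.72 / 0.71 |
| 0.5 | 0.65 / 0.73 | 0.74 / 0.64 |
| 1 | 0.51 / 0.79 | 0.79 / 0.50 |
| 2 | 0.22 / 0.90 | 0.90 / 0.21 |

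The direction of error reverses with the campaign that Aim 3 resembles. The Aim 3 c-statistic was essentially the same in both columns: 0.79, 0.76, about 0.72 and about 0.64. A shift common to all patients cancels, and only discrimination is lost.

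**The case against.** The best defence is that nothing in the documents shows a campaign effect. All recordings pass through common pre-processing, both Aim 1 sources are recorded with concurrent VF, and the plan repeats the same analyses on both sets. Varied conditions across patients argue against one uniform signature of the earlier campaign. The Table 1 remark concerns other studies, and the remark on conditions unique to each patient describes a 53-patient pilot. A1.e and A1.f also use VF-based targets that vary within patients, and Aim 2 models graded scores.

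Most of this stands, and it makes the point an uncontrolled risk, not a demonstrated bias. It does not show that the risk is absent: pre-processing may shrink a campaign difference, but the plan does not check that it does.

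Three stronger readings are tempting and are not supported:

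- A reader might infer that Aim 3 patients, being newly recorded, would look healthy and OPD would be missed. That needs Aim 3 recordings to carry the healthy-campaign signature. Aim 3 records water swallows during the SIS with VF separate, which is a third setting, so either direction of error is possible. The planned A3.e comparison uses c-statistics, which a common shift does not move.
- A reader might infer that no healthy person was recorded in 2013-2018. The A1.c pilot had 55 healthy participants whose recording dates are not given. The documents support only that the pooled Aim 1 data contain no healthy recordings from the earlier grant.
- A reader might infer that the network works on raw signals. STEPS 3 and 4 refer to pre-processed recordings and signal features.

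**Conclusion.** The concern holds as a gap in design and validation. For STEP 5 the alias between class and campaign is complete; for the PAS and VF-score targets in A1.e and A1.f it is partial. No planned validation step can separate swallowing from recording conditions, so a high hold-out accuracy would not by itself establish swallow discrimination.

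The size is conditional. It rests on an assumed campaign shift, independent cues, a true c of 0.70 and, for Aim 3, the same swallow signal separating OPD from non-OPD patients. On those terms, the gap between apparent Aim 1 c and c within one campaign is 0.74 against 0.67 at 0.5 SD and 0.93 against 0.57 at 2 SD. If the shift is zero there is no bias, but the plan as written could not show that. The loss matters for Aim 3 because A3.h has 80% power only for an increase of 0.240 over an SIS c of 0.600, that is, for a c of 0.840.

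**What to change.** 1. In A1.e and A1.f, report accuracy for PAS 1-2 versus 3-8 within the patient database alone, next to the pooled result. This contrast is free of the healthy/patient campaign alias and uses the PAS grouping already adopted in A2.c. State for each accuracy figure which label it refers to, since STEP 5, A1.e and A1.f name different ones.
2. State in A1.e that pooled healthy-versus-patient accuracy will not be presented as swallow discrimination on the strength of the hold-out alone.
3. As a supporting diagnostic, where pre-swallow segments are available, run the same training and validation pipeline on them and report the healthy-versus-patient c with its confidence interval. An interval that excludes 0.5 should prompt investigation and a stated caveat before the algorithm is carried to Aim 3. It should not be an automatic block, because breathing, posture or illness can differ genuinely between the groups. An interval that includes 0.5 is not full reassurance either, since a gain or sensor-response change may not show in quiet segments.

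The cost is a little extra analysis of recordings that the study holds or will collect. The downside is that the headline accuracy may be lower. Recording some patients and some controls in the same campaign would address the alias more directly, but it needs new data collection.
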